This trial will be conducted in compliance with the protocol, International Conference on Harmonisation (ICH) guideline E6: Good Clinical Practice: Consolidated Guideline and the applicable regulatory requirements from Title 45 of the Code of Federal Regulations (CFR) Part 46 and 21 CFR parts 50 (informed consent) and 56 (institutional review board (IRB) and 312 (Investigational New Drug Application IND).

All individuals responsible for the design and conduct of this study have completed Human Participants Protection Training and are qualified to be conducting this research prior to the enrollment of any participants.

INVESTIGATOR STATEMENT

I have read the protocol and agree to conduct the study as outlined and in accordance with all applicable local, state, and federal regulation.

I agree to maintain the confidentiality of all information received or developed in connection with this protocol.

Signature of Principal Investigator

Date

Name of Principal Investigator (printed or typed)

Protocol Title	"A Phase 2a Study to Evaluate the Kappa Opioid Receptor as a Target for the					
	Treatment of Mood and Anxiety Spectrum Disorders by Evaluation of Whether					
	CERC-501 Engages Key Neural Circuitry Related to the Hedonic Response"					
	Trial					
Product	CERC-501, previous research name LY2456302					
Objectives	Primary					
	• Evaluate the impact of CERC-501 10 mg relative to PBO on reward-					
	related neural circuitry in terms of ventral striatal fMRI activation during					
	anticipation of reward during the Monetary Incentive Delay (MID) Task.					
	Secondary					
	Clinical Anhedonia Measure : To determine if 10 mg of CERC-501 is					
	superior to PBO in improving a clinical self-report measure of anhedonia					
	the Snaith Hamilton Pleasure Scale (SHAPS)					
	 Behavioral Anhedonia Measure: To evaluate the impact of CERC-501 					
	relative to PBO on a behavioral measure of anhedonia the Probabilistic					
	Reward Task (PRT)					
Exploratory	To assess the effects of CERC-501 relative to placebo on:					
Objectives	• Ventral striatal fMRI activation during anticipation of loss during the					
	MID Task					
	• Resting state delta EEG current density in the rostral anterior cingulate.					
	Resting state fMRI connectivity					
	• Self-rated affective responses to cues and feedback during the MID Task					
	• The Effort-Expenditure for Rewards Task (EEfRT)					
	• The Visual Analogue Scale for Anhedonia (VAS)					
	• The Temporal Experience of Pleasure Scale (TEPS)					
	• The Hamilton Depression Rating Scale (HAM-D)					
	• The Hamilton Anxiety Scale (HAM-A)					
	• The Cognitive and Physical Functioning Questionnaire (CPFQ)					
	To assess the safety and tolerability of CERC-501 on systematically collected					
	and spontaneously reported adverse events.					
Study Design	Double-Blind, Placebo-Controlled Multi-Site Trial					
Study	Patients with mood and anxiety disorders and anhedonia; age 21 – 65 years					
Population	inclusive					
Number of	90					
Participants						
Duration of	A total of up to 16 weeks					
Participant	Up to 30 days for screening, 8 weeks of treatment and 4 weeks for a follow-up					
Participation						
Dose Schedule	10 mg CERC-501 daily for 8 weeks					
Estimated Start	May, 2015					
Estimated End	April 201 /					

PRÉCIS (Protocol Synopsis)

Table of Contents

TREETS (Trotocor Synopsis)	4
LIST OF ABBREVIATIONS	8
1. BACKGROUND AND SIGNIFICANCE	9

17. ALTERNATIVES TO PARTICIPATION	. 60
18. CONFLICT OF INTEREST	. 60
18.1. Distribution of NIH Guidelines	. 60
18.2. Conflict of Interest	. 60
18.3. Role of a Commercial Company or Sponsor	. 60
19. TECHNOLOGY TRANSFER	. 60
20. RESEARCH AND TRAVEL COMPENSATION	. 60

21. REFERENCES	. 61
APPENDICES	. 69
Appendix 1. Eligibility Checklist	. 70
Appendix 2. List of Prohibited Medications	. 72

LIST OF ABBREVIATIONS

AE	Adverse Event
CGI-I	Clinical Global Impression-Improvement
CGI-S	Clinical Global Impression-Severity
CPFQ	The Cognitive and Physical Functioning Questionnaire
CSSRS	Columbia Suicide Severity Rating Scale
DCRI	Duke Clinical Research Institute
DSMB	Data Safety Monitoring Board
EDC	Electronic Data Capture
EEfRT	Effort Expenditure for Rewards Task
EEG	Electroencephalogram
FDA	United States Food and Drug Administration
fMRI	Functional Magnetic Resonance Imaging
HAM-A	Hamilton Rating Scale for Anxiety
HAM-D	Hamilton Rating Scale for Depression
HIPPA	Health Insurance Portability and Accountability Act
HSP	Human Subjects Protection
KOR	Kappa Opioid Receptor
CERC-501	Investigational Kappa Opioid Receptor Antagonist
MID	Monetary Incentive Delay Task
MINI	Mini International Neuropsychiatric Interview (Mental State Examination)
MRI	Magnetic Resonance Imaging
NIMH	National Institute of Mental Health
PBO	Placebo
PHI	Protected Health Information
РК	Pharmacokinetic
POC	Proof of Concept
PRISE	Patient Reported Inventory of Side-Effects
PRT	Probabilistic Reward Task
RDoC	Research Domain Criteria Project
SAE	Serious Adverse Event
SHAPS	Snaith-Hamilton Pleasure Scale
TEPS	Temporal Experience of Pleasure Scale
VAS	Visual Analogue Scale

1. BACKGROUND AND SIGNIFICANCE

1.1. Overview

This Phase 2A study is a double-blind, placebo-controlled, randomized, parallel-group, 6site, trial of 8 weeks of daily dosing with 10 mg of CERC-501 (LY2456302) that is intended to test whether we can establish Proof of Concept (POC) that kappa opioid receptor (KOR) antagonists engage neural circuits involved in mediating the reward response. This will be specifically determined by testing whether CERC-501, a relatively selective KOR antagonist, increases ventral striatal activation in response to rewardpredicting cues. We are attempting to establish POC in this study in order to determine whether there is a sufficient basis for pursuing future work evaluating whether KOR antagonism has therapeutic effects on clinical and behavioral measures of reward-related functioning, a domain of function that is impaired in many patients with Mood and Anxiety Spectrum Disorders.

The primary outcome measure which is being used to establish POC is neural activation within the ventral striatum during the Monetary Incentive Delay (MID) Task, as assessed with fMRI (Wacker et al., 2009; Pizzagalli et al., 2004, 2008a, 2009; Treadway et al., 2012; Stoy et al., 2012; Ossewaarde et al., 2011; Knutson et al., 2008). This study also includes a number of secondary and exploratory measures to assess various domains of reward-related function including: the Snaith-Hamilton Pleasure Scale (SHAPS), a selfreport assessment of global reward function (Gilbert et al., 2002; Snaith et al., 1995); the Probabilistic Reward Task (PRT), an objective behavioral assessment of the capacity to learn from rewards (Barr et al., 2008; Bogdan and Pizzagalli, 2006, 2009; Pizzagalli et al., 2005, 2007, 2008a; Vrieze et al., 2013); the Effort-Expenditure for Rewards Task (EERT), a behavioral measure of the extent to which an individual is motivated by reward (Treadway et al., 2009, 2012a,b); the Temporal Experience of Pleasure Scale (TEPS), a self-report measure that assesses anticipatory pleasure ('wanting') and consummatory pleasure ('liking') (Gard et al., 2006; Stanford et al., 2011); a visual analogue scale (VAS) rating of hedonic respone; an additional measure of the engagement of neural circuits mediating the hedonic response, resting qEEG current density measures of delta power (Wacker et al., 2009; Pizzagalli et al., 2004); and selfratings of the reward response to stimuli in terms of ratings of affective responses to cues and feedback during the Monetary Incentive Delay Task (Pizzagalli et al., 2009). All of these are exploratory measures except the SHAPS and the PRT, which have previously been shown to be modulated by dopamine, affected by stress, associated with striatal function, predictive of clinical outcome and anhedonic symptoms, and improved with antidepressant therapy (Bogdan et al., 2011; Pizzagalli et al., 2005, 2008a,b, 2009; Santesso et al., 2008; Vrieze et al., 2013a,b; Di Giannantonio and Martinotti, 2012; Martinotti et al., 2011; Wacker et al., 2009). Other measures included in this study are: assessment for adverse effects, the Cognitive and Physical Functioning Questionnaire (CPFQ), and traditional anxiety (Hamilton Rating Scale for Anxiety [HAM-A]) and depression (Hamilton Rating Scale for Depression [HAM-D] measures, which are being evaluated in exploratory analyses to provide information regarding changes in depression and anxiety severity with treatment (Hamilton 1960, 1967; Fava et al., 2009).

1.2. Background

The available treatments for patients with mood and anxiety disorders have significant limitations (Rush, 2007; Denys and de Geus, 2005). There is a need to develop new treatments for people with these disorders. Many research studies carried out in animals and a few preliminary studies carried out in humans suggest that medications which block kappa opioid receptors (KOR) have potential for being effective new treatments for patients with mood and anxiety spectrum disorders (see below). These medications have shown particular promise for improving one important type of difficulty experienced by many patients who suffer from mood and anxiety spectrum disorders referred to as anhedonia, which is an impairment in reward-related function. In this study we will test the hypothesis that KOR antagonism is a promising means of improving anhedonia in patients with mood and anxiety spectrum disorders. We will do so by evaluating whether we can establish Proof of Concept (POC) that a relatively selective KOR antagonist, CERC-501 (LY2456302; see Investigator Brochure), engages neural circuits involved in mediating reward-related function in patients with mood and anxiety spectrum disorders with anhedonia. We are attempting to establish POC in this study in order to determine whether there is a sufficient basis for pursuing future work evaluating whether KOR antagonism has therapeutic effects on clinical and behavioral measures of reward-related functioning.

In addition to being a relatively selective KOR antagonist, CERC-501 is also well-suited for this study based on its pharmacologic and safety profiles (see Investigator Brochure). The 10 mg dosage of CERC-501 was chosen for evaluation because of preclinical studies, single and multiple ascending dose studies in humans, a single-dose PET study of KOR occupancy (Zheng et al., 2013), and pupillometry data obtained following administration of the mu agonist fentanyl (see Investigator Brochure). The following sections include details of the rationale for this study.

1.2.1. KOR Antagonism Promising Target for Treating Mood and Anxiety Disorders

There is an extensive set of pre-clinical studies suggesting that KOR antagonists are likely to have therapeutic effects in those with mood and anxiety spectrum disorders. This includes studies indicating a role of the kappa opiate system in mediating both anxiety and depression symptoms and studies suggesting that KOR antagonists have effects on animal models of both major depression and anxiety.

A number of studies indicate that the kappa opiate system is critical for mediating the adverse effects of stress. An important aspect of stress-related pharmacology is the dynorphins, a group of opioid peptides that exert their effects primarily through binding to KOR (Bruchas et al., 2009). Evidence suggests that stress leads to anxiety by CRF1 receptor activation of dynorphins in the basolateral amygdala which then bind to KOR (Bruchas et al., 2009). Place aversion and social avoidance occurring with repeated stress is mediated via dynorphin activation in ventral striatum, an effect which can be mimicked by KOR agonists and blocked by KOR antagonists (Land et al., 2009; Schindler et al., 2012). KOR antagonists also block stress-related impairment in elevated plus maze spontaneous exploration (Peters et al., 2011).

Non-stress anxiety paradigms also suggest that KOR antagonists are likely to have anxiolytic effects. Prodynorphin knockouts (prodynorphin is the precursor protein for dynorphins) and KOR antagonists have been found to have anxiolytic-like effects in the novelty-induced hypophagia test, the defensive burying tests, the elevated plus maze test, fear-potentiated startle test, open-field test, and light-dark test (Carr and Lucki, 2010; Knoll et al., 2011; Wittmann et al., 2009).

A larger literature suggests that KOR antagonists are likely to have anti-depressant effects and may prevent the depression-like consequences of stress. Dynorphin mediates the dysphoric aspects of stress via binding to KOR and this effect is prevented by knocking out dynorphin or administering a KOR antagonist (Land et al., 2008). The depression-like behaviors caused by chronic stress, uncontrollable stress, and social-defeat stress are mediated by kappa opiate receptors and can be mimicked by KOR agonists (McLaughlin et al., 2006; Knoll and Carlezon, 2010). KOR antagonist treated mice and KOR knockout mice show a reduction of stress-induced depression-like behavior (McLaughlin et al., 2006; Knoll and Carlezon, 2010). Stress has also been found to trigger KOR activation of dorsal raphe neurons which project to nucleus accumbens and decrease dopamine release thereby diminishing reward and increasing drug seeking (Lemos et al., 2012).

More generally, rodent studies show that administering KOR antagonists or knocking out the prodynorphin gene leads to antidepressant-like effects as assessed by reduced immobility in the forced swim test and reduced learned helplessness (via nucleus accumbens and hippocampal mediated mechanisms), whereas KOR agonists have depressogenic effects in conjunction with decreasing nucleus accumbens dopamine release (Reindl et al., 2008; Shirayama et al., 2004; Carlezon et al., 2006; McLaughlin et al., 2003; Mague et al., 2003; Todtenkopf et al., 2004; Chartoff et al., 2012; Chartoff et al., 2009).

Perhaps the best recognized effect of KOR antagonists in animal models is to prevent the development of anhedonic-like states. The literature suggesting that KOR antagonists have such effects speaks to the potential of these agents to have therapeutic effects on anhedonia in humans, which is a core symptom of mood and anxiety disorders that cuts across diagnostic boundaries. In this regard, there is evidence that KOR stimulation inhibits dopamine release in the striatum (nucleus accumbens and caudate) and induces a negative mood state (Bruijnzeel, 2009). Consistent with this model, a series of studies indicate that KOR agonists decrease phasic dopamine release in the nucleus accumbens and increase intracranial self-stimulation (a model of anhedonia), whereas KOR antagonists have the opposite effect, increasing nucleus accumbens dopamine release and decreasing self-stimulation (Ebner et al., 2010; Muschamp et al., 2011; Carlezon et al., 2006; Maisonneuve et al., 1994). Further, KOR agonists block cocaine's anti-anhedonic effect on intracranial self-stimulation (Tomasiewicz et al., 2008) and block the reinforcing/rewarding effects on drugs of abuse (Wee and Koob, 2010), whereas, giving a KOR antagonist prior to cocaine withdrawal prevented anhedonic-like intracranial selfstimulation responses (Chartoff et al., 2012).

Although data in humans on the effects of selective KOR antagonists are lacking, preliminary data from humans are consistent with the animal data in suggesting that this

target is likely to have therapeutic effects in mood and anxiety spectrum disorders. In an open-label study, 6 patients who had failed antidepressant medications and ECT were found to improve with buprenorphine (a KOR antagonist and partial mu agonist) treatment (Nyhuis et al., 2008). Findings of a double-blind, placebo-controlled, pilot study in 32 patients with treatment-resistant depression treated with the combination of buprenorphine and a mu receptor antagonist (simulated kappa opiate receptor antagonist) indicate that this combination had a significant antidepressant effect (Ehrich, 2012).

Together, the available data provide a compelling indication that KOR antagonists are likely to have therapeutic effects in patients with mood and anxiety spectrum disorders. These data point to the adverse effects of stress and particularly anhedonia as therapeutic targets of interest with these agents.

1.2.2. Rationale for Studying Effects of KOR Antagonist on Anhedonia

We chose to focus on anhedonia as an endpoint for this study because: 1) the available data suggest that anhedonia is the dimension of mood and anxiety spectrum disorders that is most likely to be improved by KOR antagonists (see above); 2) anhedonia is associated with measurable neurobiological mechanisms which can be studied with available methodologies that could be used to establish POC in terms of engagement of relevant neural circuitry (Wacker et al., 2009; Pizzagalli et al., 2004, 2009; Treadway et al., 2012; Stoy et al., 2012; Ossewaarde et al., 2011); and 3) anhedonia allows us to accomplish our goal of studying an important aspect of dysfunction that cuts across mood and anxiety spectrum disorders, consistent with the NIMH's RDoC framework.

The data indicating that KOR antagonists are likely to improve anhedonia are strong relative to the data indicating that there will be other therapeutic effects of KOR antagonists. As a result, it seems likely that, if there are any therapeutic effects of these agents in those with mood and anxiety spectrum disorders, a therapeutic effect on anhedonia would be evident. As a result, anhedonia is an appropriate primary endpoint for a POC study with a KOR antagonist the treatment of patients with mood and anxiety spectrum disorders. Failure to demonstrate a therapeutic effect of a KOR antagonist on the neural circuitry related to anhedonia using a dosage that had been demonstrated to have acceptable kappa opiate receptor occupancy would be a reasonable indication to fail KOR antagonism as a treatment for mood and anxiety disorders.

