9.1.2. Planned analyses and statistical methodology to be used

We will employ "Intention-to-Treat" (ITT) principles. Statistical tests will be performed based on a two-sided test at the 5% level of significance. Supporting analyses will also be performed. A "per protocol" analysis will restrict the analysis to participants who receive minimal exposure to the intervention, have a minimal number of longitudinal evaluations, and/or are free of major protocol violations. A "completer" analysis will only include participants who completed acute treatment without exiting or prematurely terminating from their assigned treatment. Because participants may be removed differentially across the treatment arms in these analyses, both approaches are vulnerable to differential selection bias and will be interpreted cautiously.

Most of the study outcomes are observed repeatedly at well-defined time-points postrandomization, so that statistical methods for repeated measures data will be applied. This includes the linear model with structured covariance matrices and the mixed effects models as implemented in PROC MIXED in SAS. Site will also be included as an independent variable in order to account for variability among the study sites.

Covariates in Regression Models: The baseline value of the outcome, centered about its sample mean, will be included in each analysis. Otherwise, only age and sex will be entered as covariates.

Missing Values: We will proactively monitor the amount of missing data, and ensure that we respond quickly to emerging problems. Statistically, missing data will be addressed through the use of mixed models analysis which will be carried out with PROC MIXED in SAS. We will carry out an assessment of the degree to which the structured covariance matrix in mixed effects models fits the data.

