Other Confounders Arising Post-Randomization: Logistic regression analysis will be carried out to investigate: (a) adherence to the assigned study intervention (this will include serum levels of study drug and blister pack check data), (b) co-administration of psychotropic medications, and (c) discontinuation from the study intervention. First, we will determine whether these effects occur differentially across the treatment arms suggesting that a differential selection bias may have influenced the results. Then, we will investigate whether baseline characteristics are predictive of any behavior. This will include demographic characteristics, initial severity as measured by the baseline values of the outcome variables, and clinical characteristics such as diagnoses and medications taken at baseline.

Magnitude of the Clinical Effect: To evaluate the clinical significance of the impact of treatment on outcome, effect sizes (Hedge's g) will be calculated as (ME - MC) / SD pooled, where ME represents the adjusted mean of experimental treatment, MC represents the adjusted mean of the comparison treatment, and SD pooled represents pooling of the standard deviations from within both groups. We will also assess how the estimated magnitude of treatment effect and the estimated standard deviation deviate from those postulated in sample size planning.

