9.1.2.1. Primary Analysis

Point estimate and the corresponding confidence interval for the primary study outcome (fMRI ventral striatal activation during reward anticipation of reward during the MID) of

the adjusted predicted score will be obtained. A mixed effects model analysis will be carried out for the primary outcome of the study, task-related fMRI activation in the ventral striatum during anticipation of reward occurring during the Monetary Incentive Delay Task. This analysis will test the hypothesis that CERC-501 will lead to a greater increase in ventral striatal activation during anticipation of reward than placebo.

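### Does the plan need a formal rule for when a null primary result counts against the kappa opioid target?

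*Protocol*

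**What the plan says.** The rationale for choosing anhedonia (Protocol 1.2.2, same wording in SAP 2.2) ends by saying that failure to show an effect on the related circuitry "would be a reasonable indication to fail KOR antagonism as a treatment for mood and anxiety disorders". It attaches one condition: the test must be made "using a dosage that had been demonstrated to have acceptable kappa opiate receptor occupancy". Protocol 1.1 states the purpose of the trial more softly, as determining "whether there is a sufficient basis for pursuing future work evaluating whether KOR antagonism has therapeutic effects".

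The analysis text is separate from this:

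- Section 9.1.2 on testing: "Statistical tests will be performed based on a two-sided test at the 5% level of significance".
- Section 9.1.2 on covariates: "The baseline value of the outcome, centered about its sample mean, will be included in each analysis".
- Section 9.1.2.1 on the primary outcome: "Point estimate and the corresponding confidence interval for the primary study outcome" will be obtained.
- Section 9.1.2 on effect magnitude plans Hedges' g, where "SD pooled represents pooling of the standard deviations from within both groups", and adds: "We will also assess how the estimated magnitude of treatment effect and the estimated standard deviation deviate from those postulated in sample size planning".

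Section 9.2 gives 80% power for an effect size of 0.58 with 72 complete subjects, using a one-tailed 5% t-test. It does not name a smallest effect worth pursuing. The SAP text available here ends at section 2.2, before any analysis section.

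**The concern.** Read literally, the sentence in 1.2.2 draws a conclusion about a whole drug target from a failure to demonstrate an effect in one trial of 90 subjects. Its only condition concerns whether the dose tests the target. It does not ask whether the estimate is precise enough to rule out an effect of interest.

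If every non-significant primary result were taken as failure, an imprecise null would be treated like an informative one, and a useful target could be abandoned on weak evidence. No text seen here says how the planned interval or Hedges' g bears on that conclusion.

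**Working it through.** **Inputs.** 90 randomised 1:1, 72 in the worst case, so 45 or 36 per arm (9.2). Effect sizes 0.58 and 0.50 are the detectable values in 9.2; 0.88 is its estimate from a prior open-label escitalopram study, which 9.2 calls likely too optimistic. An effect of 0.30 and the baseline-outcome correlations rho are assumptions.

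**Reproducing the plan's power.** With n per arm, the normal approximation is power = Φ(d√(n/2) − z).

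- d = 0.58, n = 36, one-sided 5%: Φ(0.58 × √18 − 1.645) = Φ(0.816) = 79.3% (noncentral t, 78.6%).
- d = 0.50, n = 36, one-sided 10%: Φ(0.50 × √18 − 1.282) = Φ(0.840) = 80.0% (noncentral t, 79.6%).
- d = 0.58, n = 36, two-sided 5%: Φ(2.461 − 1.960) = Φ(0.501) = 69.2% (noncentral t, 68.0%).

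So 9.2 reproduces as one-sided. Its difference from the two-sided test in 9.1.2 is a separate matter.

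**Precision, unadjusted.** Half-width of the 95% interval = t(0.975, 2n − 2) × √(2/n).

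- n = 36: 1.994 × 0.2357 = 0.470. Non-significant but not excluding 0.58: observed d from 0.58 − 0.470 = 0.11 up to 0.47.
- n = 45: 1.987 × 0.2108 = 0.419. The same range is 0.16 to 0.42.

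**Chance of a non-significant result (noncentral t, 72 / 90 evaluable).**

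| True d | Two-sided 5% | One-sided 5% |
|---|---|---|
| 0.50 | 45% / 35% | 32% / 24% |
| 0.58 | 32% / 22% | 21% / 14% |
| 0.88 | 4% / 1.5% | 2% / 0.6% |

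At 0.58, about 11 and 8 percentage points of the two-sided figures come only from the one- versus two-sided difference.

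**Effect of the planned baseline adjustment.** If d is in week-8 SD units, the effective size is d/√(1 − rho²). If it is in change-score SD units, it is d/√((1 + rho)/2). Two-sided miss rate at 0.58 for rho = 0.3 / 0.5 / 0.7:

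- Week-8 units: 28 / 20 / 8% with 72, and 19 / 12 / 3% with 90.
- Change units: 15 / 20 / 25% with 72, and 8 / 12 / 16% with 90.

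The documents give neither rho nor the SD scale. The miss rate could therefore lie anywhere from 3% to 28% over these cases, and its trend with rho reverses between scales.

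**What a formal rule would do.** Suppose a null counted against the target only if the 95% interval lay wholly below 0.58, with other non-significant results called inconclusive. Simulated unadjusted rates (1,000,000 trials per cell, 72 / 90 evaluable):

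- True d = 0: inconclusive about 30% / 20%.
- True d = 0.30: inconclusive about 55% / 45%, called negative 21% / 25%.
- True d = 0.58: inconclusive about 30% / 20%, called negative about 2%.
- With a margin of 0.50 instead, inconclusive at d = 0 rises to 42% / 33%.

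Under baseline adjustment, inconclusive results fall to 5 to 26% / 1 to 16% at d = 0 and 21 to 51% / 7 to 41% at d = 0.30. But a true 0.30 is then called negative more often. For 72 evaluable in week-8 units:

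- rho = 0.3, half-width 0.448: Φ((0.58 − 0.448 − 0.30)/(0.2357 × 0.954)) = Φ(−0.75) = 23%.
- rho = 0.7, half-width 0.336: Φ((0.58 − 0.336 − 0.30)/(0.2357 × 0.714)) = Φ(−0.33) = 37%.

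Over all the rho-and-scale cases the range is 23 to 37% with 72 and 28 to 42% with 90.

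**The case for a change.** The best argument for a change is that 1.2.2 is the only text seen here that says what a null would mean, and that a reading fixed before the data is more credible than one chosen afterwards. The precision problem is real at this sample size, and baseline adjustment reduces it without removing it. With a 0.58 margin, a true 0.58 would be called negative about 2% of the time, unadjusted, instead of 32% or 22% if every non-significant result meant failure. The primary test, the sample size and the chance of a positive result would all stay the same.

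The arithmetic stands, and so does the observation that the available text sets no threshold. Three parts of the argument do not carry through:

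- The 32% and 22% count as wrong decisions only if failure to demonstrate means non-significance and non-significance means abandoning the target. Section 1.2.2 says neither.
- The absence of a criterion cannot be established. The place for one is the SAP's analysis sections, which were not available here.
- The rule's decisive number is missing. The 0.58 is what 9.2 says can be detected, not a minimum relevant effect, and the documents offer no other margin.

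**Conclusion.** No change follows. The sentence in 1.2.2 and SAP 2.2 is hedged rationale for choosing the endpoint, tied to receptor occupancy. It sets no decision rule, and section 1.1 frames the aim as whether further work is justified.

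A competent analyst fills the gap from what is already planned. The primary interval shows which effects remain plausible, and section 9.1.2 requires the observed effect and SD to be compared with the planning values. A null whose interval still contains 0.58 would be visible in that report. Section 9.1.2.1 refers to the adjusted score, but the hypothesis it tests is a greater increase than on placebo, so the natural reading of the interval is the adjusted between-arm difference.

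A formal margin would exchange one kind of ambiguous outcome for another. At 0.58, unadjusted, it makes 20 to 30% of true nulls and 45 to 55% of trials with a true 0.30 inconclusive. With adjustment it calls a true 0.30 negative in 23 to 37% (72 evaluable) or 28 to 42% (90) of trials. Whether that is better for a 90-subject proof-of-concept study is a matter of judgement.

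These sizes rest on a two-group comparison in SD units, 36 or 45 evaluable per arm, and assumed rho of 0.3 to 0.7. The conclusion would need another look if the SAP's analysis sections made the sentence in 1.2.2 a formal stopping criterion for the target.
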